[name]
[name]
P: [contact] F: [contact]
[contact]

Laboratories

Principal Investigator: [name]
Institute for Genomic Sciences
University of Maryland Baltimore
Baltimore, MD
[contact]

Co-Investigator: [name]
School of Pharmacy
University of Maryland Baltimore
Baltimore, MD
[contact]

Biostatistician: [name]
School of Public Health
University of Maryland Baltimore
Baltimore, MD
[contact]

PRÉCIS

Study Title: Exploratory Pilot Studies to Demonstrate Mechanisms of Preventing Antibiotic- Associated Diarrhea and the Role for Probiotics

Phase: Mechanistic Study

Population: 60 healthy adults ages 18-65 years

Number of Sites: Single Center

Study Duration: R61 Phase: 24 months

Description of Study Design: Randomized, double-blinded, controlled clinical trial

National Clinical Trial (NCT) Number: NCT03755765

Georgetown University Institutional Review Number: 2018-0736

Primary Objective:

To determine the ability of BB-12 to impact antibiotic-induced reduction in SCFA concentration as reflected by the levels of acetate on day 7. SCFA produced by anaerobic gut microbiota will be quantified from human fecal samples via liquid chromatography-tandem mass spectrometry (LC-MS/MS).

Secondary Objective:

To determine the ability of BB-12 to impact antibiotic-induced disruption of the gut microbiota with 16S rDNA profiling. This will be assessed at days 7 and 14. Changes in absolute abundance of specific bacterial genera (with a particular emphasis on known butyrate producers in the Firmicutes phylum) will also be assessed with qPCR.

Design and Outcomes:

This is a randomized, double-blinded, single center, mechanistic study to test the mechanism of *Bifidobacterium animalis* subsp. *lactis* (B. *lactis*) strain BB-12 (BB-12) yogurt in AAD, compared to yogurt without BB-12, in healthy adults. Sixty participants will be randomized to two groups, BB-12 supplemented yogurt (40) and control yogurt (20), using a 2:1 random allocation rule. All participants will be given a 7-day prescription for 875/125 mg of amoxicillin-clavulanate (AMC), taken twice daily. Participants will be recruited through the Capital Area Primary Care Research Network (CAPRICORN), a practice-based research network (PBRN), and other community sites.

Interventions and Duration:

[figure not shown]
The probiotic-supplemented yogurt is composed of the investigational agent, BB-12, and contains the yogurt starter culture YF-L702 (a mixed culture of *Streptococcus thermophilus* and *Lactobacillus delbrueckii* subsp. *bulgaricus*). The yogurt starter culture will be present and alive in the control yogurt. Participants are to provide informed consent at Baseline and complete a 30-day run-in period, during which they will refrain from all probiotics, and begin the antibiotic and yogurt interventions on Day 1.

Participants will be randomized to receive BB-12-supplemented yogurt or control yogurt (without BB-12), in a 2:1 (40:20 participants) allocation (**Figure 1**).

Group 1 (n=40): Probiotic, BB-12-supplemented yogurt, 4-ounces (which delivers $\geq 10^{10}$ CFU of BB-12) taken orally for 14 days and amoxicillin-clavulanate 875/125 mg, twice daily, for 7 days.

Group 2 (n=20): Control yogurt, 4-ounces taken orally for 14 days and amoxicillin-clavulanate 875/125 mg, twice daily, for 7 days.

Figure 1.

Fecal samples will be collected at home (at baseline (pre and post run-in), days 7, 14, 21 and 30) for SCFA and microbiome testing. Participants will be given detailed, written and illustrated instructions on proper sample collection procedures, and research staff will review these protocols with participants during enrollment.

Follow-up phone visits will be completed on Days 7, 14, and 30. Participants will keep a daily diary to track number, shape and consistency of bowel movements, if/when antibiotic and/or yogurt was consumed, Bristol Stool chart, general health, use of other medicines or products, adverse events, and the Gastrointestinal Symptom Rating Scale (GSRS) - Irritable Bowel Syndrome (IBS) version..

Duration: Each participant will be in the study for approximately 8 weeks total. During the first 30 days, the participant will refrain from antibiotics and probiotics (run-in period) and provide two baseline samples. The participant will be taking the antibiotic intervention for 7 days and taking the yogurt intervention for 14 days. There are two more data collection visits on day 21 and 30.

Pre run-in Baseline	Run-in (30 days)	Post run-in Day 0	Day 1	Day 7	Day 14	Day 21	Day 30
Informed Consent	No antibiotics	Fecal sample	AMC start	AMC end	Yogurt end	Fecal sample	Fecal sample
Inclusion/exclusion	No probiotics	Post-run in inclusion/exclusion	Yogurt start	GSRS-IBS	Diary end		
Enrollment		Post run-in health status	Diary start	Fecal sample	GSRS-IBS		
Demographics		Randomization		Follow-up	Fecal sample		
Baseline health					Follow-up		
GSRS-IBS							
Fecal sample							

Sample Size and Population:

The population will be generally healthy adults of ages 18-65 years. This randomized controlled trial is open to all eligible adults who meet the inclusion criteria. We are not proposing exclusion of any specific sex/gender or racial/ethnic group. One hundred participants will be recruited from the greater community and clinical sites in the Washington, DC metropolitan area, and sixty (n=60) participants will be randomized and commence the study. Based on the demographics of the network and recruitment rates in previous studies at our site, we anticipate about 50% of participants will be women, 20% will be Spanish speakers, and 30-40% will self-identify as one of the racial or ethnic minority populations.

1. STUDY OBJECTIVES

1.1 Primary Objective

To determine the ability of BB-12 to impact antibiotic-induced reduction in SCFA concentration as reflected by the levels of acetate on day 7. SCFA produced by anaerobic gut microbiota will be quantified from human fecal samples via liquid chromatography-tandem mass spectrometry (LC-MS/MS).

Primary Hypothesis: Antibiotics will result in a reduction in fecal SCFA by day 7. BB-12 supplementation will protect against antibiotic-induced SCFA reduction and/or be associated with a quicker return to baseline SCFA levels, as compared to the control group.

1.2 Secondary Objectives

To determine the ability of BB-12 to impact antibiotic-induced disruption of the gut microbiota with 16S rDNA profiling. This will be assessed at days 7 and 14. Changes in absolute abundance of specific bacterial genera (with a particular emphasis on known butyrate producers in the Firmicutes phylum) will also be assessed with qPCR.

Secondary Hypothesis: Antibiotics will result in a decrease in the overall number and diversity of bacterial species present in the fecal microbiota. This will be assessed at baseline and days 7, 14, 21 and 30, and we would expect a decrease in at least days 7 and 14. BB-12 supplementation will protect against antibiotic-induced shifts in the microbiota and/or will be associated with a quicker return to a baseline microbiota composition, as compared to the control group. Microbiota composition will be assessed with 16S rDNA profiling and qPCR.

2. BACKGROUND AND RATIONALE

2.1 Background Information

Probiotics are live microorganisms that, when administered in sufficient amounts, may improve health.(1) Often, probiotics are ingested as supplements in powder, pill or liquid forms, designed specifically for medicinal benefit. Such supplements have shown potential benefits in treatment and prevention of varied diseases, including diarrhea, asthma, necrotizing enterocolitis and allergies.(2-6) As an alternative to supplements, probiotics are also included as ingredients in fermented dairy products to produce functional foods; that is foods providing health benefits beyond their nutritional value.(7-10) Yogurt, for example, is a fermented milk product often considered a functional food. In fact, two-thirds of primary care physicians who counsel patients about nutrition recommend consuming yogurt containing live active cultures for the health benefits associated with this food.(11) Despite this common practice, however, evidence for beneficial health outcomes is limited.

2.2 Microbiota Play an Important Role in the Gastrointestinal Tract

The gastrointestinal tract contains a complex commensal microbiota that contributes to homeostasis in the gastrointestinal tract. The intestinal microbiota includes hundreds of species of facultative and obligate anaerobes.(12) The human intestine is home to over 100 trillion microorganisms. When functioning appropriately, this high-species diversity produces homeostasis of the gut.(13) This balance is often disturbed by medical interventions such as antibiotics or viral diseases, causing a disturbance of the fecal microbiota and resulting in, among other effects, decreased short chain fatty acid metabolism. This causes the accumulation of luminal carbohydrate, subsequent pH changes, and water absorption.(14) Supplemental probiotics may help regulate the microbiota when disturbed by outside influences.(15)

2.3 General *Bifidobacterium* Information

Probiotics marketed as nutritional supplements and found in functional foods, such as yogurts, are principally members of the genera *Bifidobacterium* and *Lactobacillus*. Members of these genera are Gram-positive facultative anaerobes and are also classified as lactic acid bacteria (LAB). *Bifidobacterium* species, particularly *B. lactis* BB-12, the principal focus of this study, can be found in the gastrointestinal tract (GIT) as both autochthonous (native to a particular place) and allochthonous (derived from outside a system) residents.(16) Newborns, especially those that are breast-fed, are colonized with bifidobacteria within days after birth. Once the child is weaned, the population of these bacteria in the colon appears to be relatively stable until advanced age when it appears to decline.(16, 17) Furthermore, *B. lactis*, unlike the majority of anaerobic bifidobacteria, are moderately tolerant of oxygen. It is for this reason that *B. lactis* is so extensively used for research and commercial application.(18)

2.4 Likely Mechanisms of BB-12 Health Effects

There are many potential mechanisms by which probiotics are believed to exert their effects. Possible mechanisms of probiotic effect include: 1) production of antimicrobial substances; 2) binding to and penetrating gastrointestinal receptors; 3) competition for nutrients; 4) enhancement of mucosal barrier function; 5) altered immunoregulation, including both anti-inflammatory and immunostimulatory responses; and, 6) ferment glucose, lactose, and fructose, thereby lowering fecal pH.(19-25)

Due to the immune system's role in a multitude of disease states, many studies have concentrated on the immunoregulatory effect of probiotics, examining probiotics' role in diseases, such as eczema with potential mechanisms involving T cell, B cell, epithelial cell, dendritic cell, macrophage, nature killer cell, antibody, and cytokine effects.(26-28) After providing infants who manifested atopic eczema (mean age

of 4.6 months) with a BB-12 infused formula, Isolauri, et al., found significant skin improvements in the probiotic group compared to the control group (P=0.002).(28)

Additionally, many believe that inflammatory bowel disease (IBD) appears to be caused by immune responses to commensal enteric bacteria in predisposed individuals.(24) A commercial blend of eight different probiotic strains (*Streptococcus thermophilus*, three strains of *Bifidobacterium* species and four strains of *Lactobacillus* species), VSL3, has been shown to limit epithelial inflammatory responses in vivo and in vitro, and is often prescribed for individuals with IBD.(29-34)

Further support of an immunoregulatory response is a study conducted by Fukushima et al. on healthy Japanese children between the ages of 15 and 31 months. The children were fed a follow-up formula infused with 10⁹ CFU BB-12 and were found to have a significant increase in total IgA and anti-poliovirus IgA, respectively.(35) This suggests ingestion of the probiotic formula containing BB-12 and colonization by the strain can trigger IgA production by the host. This type of data demonstrates that probiotics positively influence the maturation process of immunity.

2.5 BB-12 Survival in Stools

The ability to isolate an orally administered probiotic in the stools is considered to be a good indicator that the strain is able to reach key target sites throughout the intestinal tract. The ability of BB-12 to survive intestinal transit has been documented in several studies.(36-39) Taken together, these studies document the ability of BB-12 to survive gastrointestinal transit and persist for 1-3 weeks post feeding. However, the degree of persistence is likely due to doses fed, delivery vehicle, host factors and the ability of BB-12 to grow during colonization. Studies such as the one proposed here are needed to document the success of probiotic survival in foods supplemented with probiotics.

2.6 Safety of Use of BB-12

Lactic acid bacteria (LAB) in foods have a long history of safe use. LAB and related organisms (with the exception of enterococci) are seldom associated with infections, except in immunodeficient individuals or individuals with severe underlying illness.(40) Although bifidobacteria are not naturally found in food, they have been used as ingredients of dietary supplements and added to foods as functional ingredients for decades.(16) The BB-12 strain has been used in numerous controlled human studies in pediatric and adult populations with no adverse incidents reported. BB-12, in combination with a strain of *S. thermophilus*, was the subject of a GRAS petition to the FDA March 2002 (Agency GRAS Notice GRN 000049), where the FDA did not object to use of these bacteria in infant formula.

Although transferable antibiotic resistances are not very common among LAB, they do occur. BB-12 was evaluated for such resistance genes and was found to contain the tetracycline resistance gene *tet(W)*. Nestlé provided these data to the FDA in support of its view that the presence of *tet(W)* does not affect the safety of BB-12 as an ingredient in infant formula. In November 2005, the FDA responded to this additional information stating that:

“Based on the information provided by Nestlé, as well as other information available to FDA, the agency has no questions at this time regarding Nestlé’s conclusions that the presence of the *tet(W)* gene in their *B. lactis* strain does not affect the safety of the intended use of *B. lactis* as an ingredient in infant formula and that the discovery of the *tet(W)* gene in *B. lactis* does not change their previous conclusion that *B. lactis* is GRAS for its intended use as an ingredient in infant formula.”

A summary of the BB-12 safety articles, using the identical strain as in this protocol, is included in the **Appendix**.

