4.2 Inclusion Criteria

Participants will be *eligible* if:

1. S/he is between ages of 18-65 years
2. S/he has the ability to read, speak and write English
3. S/he has refrigerator for proper storage of the intervention
4. S/he has telephone access

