4.3 Inclusion of Women and Minorities

This is an adult study and no one under age 18 will be included. All adults who meet the inclusion/exclusion criteria, regardless of religion, sex, or ethnic background will be enrolled if they sign the informed consent.

Based on rates of patients seen in our network, we anticipate about 50% of the potential participants will be female. Many of our practices are based in the inner-city and have an over-representation of ethnic minorities.

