4.4 Exclusion Criteria

Participants will be *ineligible* if any of the following conditions are present:

1. Diabetes or asthma that requires daily medication
2. Allergy to strawberry
3. Active diarrhea (three or more loose stools per day for two consecutive days)
4. Any gastrointestinal medications, i.e. medicines for irritable bowel syndrome, gastroesophageal reflux disease, inflammatory bowel disease, etc. (a full medication list will be reviewed by the PI prior to enrollment)
5. Lactose intolerance
6. History of heart disease, including valvulopathies or cardiac surgery, any implantable device or prosthetic
7. History of gastrointestinal surgery or disease
8. Milk-protein allergy

9. Allergy to any component of the product or the yogurt vehicle
10. Allergy to penicillin or cephalosporin class antibiotics
11. Allergy to any of the following medications:
 - a. Penicillin
 - b. Erythromycin
 - c. Tetracycline
 - d. Trimethoprim
 - e. Ciprofloxacin
12. Women who are breastfeeding, pregnant, or planning to become pregnant during the study.

Participants must agree to refrain from all probiotics throughout the study, starting from the 30-day run-in period through day 30.

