6.5 Enrollment, Baseline, and Randomization

6.5.1 Enrollment

The enrollment/baseline visit will take place at the participants' homes or an office where comfort and confidentiality is assured. There is no clinic visit associated with this study. The purpose of this visit is to have in-person time to collect baseline data, explain all forms, go over the schedule of visits and intervention, and give the participant the initial compensation. No physical exams or medical assessments will be conducted as part of the screening or enrollment process.

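### Section 2.6 excepts immunodeficient and severely ill people from its safety statement on lactic acid bacteria, but the eligibility lists omit the first group and cover the second only in part

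*Combined protocol and SAP*

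**What the plan says.** Section 2.6 rests the safety of the product partly on the record of lactic acid bacteria and related organisms, which it calls "seldom associated with infections, except in immunodeficient individuals or individuals with severe underlying illness". Section 2.3 classes *Bifidobacterium* with the lactic acid bacteria, so the statement and its exception apply to BB-12.

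The Précis gives the population as "60 healthy adults ages 18-65 years". Section 4.2 has four inclusion items: age ("S/he is between ages of 18-65 years"), English, a refrigerator and a telephone. Section 4.4 has twelve numbered exclusions. Those that concern illness or medication are:

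- item 1: "Diabetes or asthma that requires daily medication"
- item 3: active diarrhea
- item 4: gastrointestinal medicines, with the note "a full medication list will be reviewed by the PI prior to enrollment"
- item 6: "History of heart disease, including valvulopathies or cardiac surgery, any implantable device or prosthetic"
- item 7: past gastrointestinal surgery or disease

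The rest are allergies, lactose intolerance, and pregnancy or breastfeeding. Section 5.3.3 bars diabetes, asthma and gastrointestinal medicines at enrollment. On screening, 6.5.1 says "No physical exams or medical assessments will be conducted as part of the screening or enrollment process".

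**The concern.** The background section names two groups for whom its reassurance is weaker, and one would expect the eligibility lists to deal with both. They do not. The omission bears on participant safety because 7.1 makes strict enforcement of the exclusion list the means of preventing adverse events, with allergy to strawberry or yogurt as its particular focus. The risk lists in 2.12.1 and 7.5 do not mention infection by the product organisms, so they would not alert staff either.

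At stake is whether someone on immunosuppressive treatment, for example, could pass every listed criterion and be given a live-culture product together with an antibiotic, with nothing in the protocol to explain why that is acceptable.

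**Working it through.** No statistical formula is involved. The check sets the passages side by side and then confirms the two figures that describe exposure.

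**Step 1. Groups named in 2.6 against the lists.**

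| Group in 2.6 | 4.2 inclusion (4 items) | 4.4 exclusion (12 items) | 5.3.3 medications |
|---|---|---|---|
| Immunodeficient | no item | no item | no immunosuppressant listed |
| Severe underlying illness | no item | in part: items 1, 4, 6 and 7 | in part: diabetes, asthma and gastrointestinal medicines |

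Cancer, kidney disease and liver disease, for example, appear in none of the three lists.

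**Step 2. Could another step catch such a person?**

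- *Healthy* or *generally healthy* appears in the Précis and in sections 3 and 10.2.3 as a description. It is not defined and is not among the criteria.
- The PI's review takes in a full medication list, but the phrase sits inside the gastrointestinal-medicine item. No ground is stated for refusing a person because of another kind of medicine.
- Under 6.5.1 there is no examination or medical assessment at screening or enrollment.
- After the run-in, 6.5.2 repeats the Inclusion/Exclusion form and adds a Post Run-In Health Status form. Withdrawal at that point is for an exclusionary medication or condition, a term that leads back to the same lists. The contents of the health-status form are not shown.

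No documented step clearly closes the gap.

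**Step 3. Exposure.** The stated dose in the active arm is at least 10^10 CFU a day. Table 6 (5.2.1.7) gives the mean log CFU/ml, and a serving is taken as 100 ml:

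- Day 0: 10^8.86 × 100 = 7.2 × 10^10 CFU
- Week 3 (lowest mean): 10^8.48 × 100 = 3.0 × 10^10 CFU
- Week 3, one SD (0.47) lower: 10^8.01 × 100 = 1.02 × 10^10 CFU

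The stated dose is reproduced at the mean. If log counts are assumed normal with the Table 6 SD, about 15% of 100 ml servings at week 3 would fall below 10^10. That does not affect this point.

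**Step 4. Allocation.** Section 6.5.3 specifies four blocks of 9 and four of 6 at 2:1:

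- BB-12: 4 × 6 + 4 × 4 = 40
- Control: 4 × 3 + 4 × 2 = 20

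A randomized person therefore has a 40/60 = two-thirds chance of receiving BB-12. The control yogurt also contains live starter culture (5.1), although 5.1 says the starter does not survive the stomach.

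**The case against.** The best defense is that the trial is described throughout as one of healthy adults, that the PI sees a full medication list before enrollment, and that no sensible investigator would enroll a patient on chemotherapy. The statement in 4.3, "All adults who meet the inclusion/exclusion criteria, regardless of religion, sex, or ethnic background will be enrolled", subject to consent, stands under a heading on women and minorities and reads most naturally as a promise not to discriminate. These points stand, and they make such an enrollment unlikely. They leave the decision to judgment that no criterion records.

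The defense can also point to Appendix 2, which cites use in fragile groups, including preterm infants and intensive-care patients. That evidence addresses such people but does not withdraw the exception in 2.6. In the intensive-care study, septic complications occurred in 33/45 (73%) on a multi-strain synbiotic and 26/45 (58%) on placebo, P=0.12. This shows neither harm nor safety for BB-12 in the severely ill.

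A reader might infer more than the documents support:

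- *That both groups are wholly missing.* Items 1, 4, 6 and 7 cover some severe illness.
- *That one infection would be an SAE and could halt the trial.* It would be an SAE only if it met a criterion in 7.3, such as hospitalization or an important medical event. Suspension under section 8 is discretionary, and its specific triggers include a possibly related death or a significant number of SAEs or hospitalizations.
- *That the post-run-in check only repeats the same list.* It also uses a health-status form whose questions are not shown.
- *That the acetate planning figures are compromised.* Nothing in the documents quantifies such an effect.

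**Conclusion.** The mismatch is real and specific. Immunodeficiency and immunosuppressive treatment are absent from 4.2, 4.4 and 5.3.3, and severe underlying illness is covered only in part. As written, the criteria could admit a person whom 2.6 excepts. The number is unknown and probably small. This is a gap in participant protection and internal consistency, with low likelihood and a potentially serious consequence; it is not a flaw in the primary analysis.

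The conclusion assumes that the listed criteria decide eligibility and that the screening forms, whose content is not shown, follow them. If those forms already ask about immune status and severe illness and give grounds for refusal, what remains is a drafting correction.

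**What to change.** Reconcile 4.2, 4.4 and 5.3.3 with 2.6. The sponsor can take either of two routes:

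- carry the groups named in 2.6 into the eligibility criteria and the existing Pre-screening and Inclusion/Exclusion forms, in terms that the sponsor defines; or
- state in the protocol why these people may be enrolled despite 2.6.

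Where the line for severe illness falls is a clinical decision for the sponsor. The cost is a protocol amendment with IRB approval (11.1), any needed change to existing forms and, under the first route, possibly a few volunteers who become ineligible. No test or visit is added.
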